# 1.4 Rationale for Obicetrapib and Ezetimibe Combination Therapy

An important therapeutic goal is to maximize LDL-C reduction for patients who cannot tolerate statin therapy. Ezetimibe selectively inhibits intestinal cholesterol absorption. Ezetimibe used as monotherapy for patients with hypercholesterolemia significantly reduces serum LDL-C levels, as evidenced by a meta-analysis of 8 randomized, double-blind, placebo-controlled studies, with a statistically significant mean reduction in LDL-C of 18.58% compared with placebo. Ezetimibe in combination with statin therapy further reduces LDL-C levels. A meta-analysis of 27 studies, including more than 21,000 patients, demonstrated a 15.1% greater reduction in LDL-C in patients treated with statin and ezetimibe in combination compared with statin alone.  Although there is a lack of evidence that ezetimibe monotherapy reduces cardiovascular events, the IMPROVE-IT study, 16 in which simvastatin 40 mg daily was compared with a combination of simvastatin 40 mg plus ezetimibe 10 mg in 18,144 patients with acute coronary syndrome, demonstrated a modest but statistically significant further reduction in future cardiovascular events (a 2% absolute risk reduction over 7 years) in the combination group compared with statins alone. These large long-term studies have also demonstrated an excellent safety profile for ezetimibe. Importantly, additional Mendelian randomization studies have revealed that the CETP inhibitor HMGCR inhibitor interaction does not occur when a CETP inhibitor is combined with ezetimibe.

Accordingly, to evaluate the potential for ezetimibe to further augment LDL-C as well as ApoB reduction achieved by a CETP inhibitor, this study will test the effect of obicetrapib and ezetimibe combination therapy compared to obicetrapib monotherapy and ezetimibe monotherapy in participants with mild dyslipidemia.

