# 9.2.1.2 Secondary and exploratory efficacy analysis

A similar MMRM model will be used for the analysis of the secondary and exploratory efficacy endpoints corresponding to the percent change from baseline. For the binary efficacy endpoints, a logistic regression analysis will be performed with model covariates of treatment group and baseline LDL-C.

In order to maintain the overall Type I error rate, the secondary efficacy endpoints will be tested sequentially at the 0.05 significance level according to the pre-specified order of hierarchy. No adjustment will be made for multiplicity in testing the exploratory efficacy endpoints. Nominal p-values will be provided when applicable. Descriptive and graphical summaries by treatment group will also be presented. Any additional sensitivity and/or supplemental analyses will be defined in the SAP.

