2.3.2 Secondary Efficacy Endpoints

The secondary efficacy endpoints include the following, in hierarchical order:

- Percent change from Day 1 to Day 57 in LDL-C for the obicetrapib monotherapy group compared to the placebo group;
- Percent change from Day 1 to Day 57 in ApoB for the combination therapy group compared to the placebo group;
- Percent change from Day 1 to Day 57 in ApoB for the obicetrapib monotherapy group compared to the placebo group;
- Percent change from Day 1 to Day 57 in LDL-C for combination therapy group compared to the ezetimibe monotherapy group;
- Percent change from Day 1 to Day 57 in LDL-C for the obicetrapib monotherapy group compared to the ezetimibe monotherapy group;
- Percent change from Day 1 to Day 57 in LDL-C, for the ezetimibe monotherapy group compared to the placebo group; and
- Percent change from Day 1 to Day 57 in ApoB for the combination therapy group compared to the ezetimibe monotherapy group.

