2.3.3 Exploratory Efficacy Endpoints

The exploratory efficacy endpoints include the following:

- Percent change from Day 1 to Day 57 in ApoB for the ezetimibe monotherapy group compared to the placebo group;
- Pairwise comparisons among the various treatment groups for the percent change from Day 1 to Day 57 in non-HDL-C, VLDL-C, HDL-C, TG, ApoE, and HDL-ApoE (with and without ApoC3);
- Pairwise comparisons among the various treatment groups for the proportion of participants at Day 57 that achieve LDL-C <2.6 mmol/L (<100 mg/dL), LDL-C <1.8 mmol/L (<70 mg/dL), and LDL-C <1.3 mmol/L (<50 mg/dL);

NewAmsterdam Pharma BV	CONFIDENTIAL	Statistical Analysis Plan
Protocol TA-8995-303		Version V2.0, 24 June 2021

- Pairwise comparisons among the various treatment groups for the change from Day 1 to Day 57, Day 1 to Week 12, and Day 1 to Week 16 in the mean trough plasma levels of obicetrapib; and
- Pairwise comparisons among the various treatment groups for the change from Day 1 to Day 57, Day 1 to Week 12, and Day 1 to Week 16 in CETP mass.

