3.4 Efficacy Assessment

The mITT Population will be the primary population for the efficacy analyses. Efficacy will also be analyzed using the ITT Population and the PP Population as supportive analyses for select endpoints.

It is to highlight that LDL-C level will be collected using the following two approaches:

- 1. At each scheduled visit, LDL-C level will be calculated using the Friedewald formula;
- 2. In addition, at Baseline (Day 1) and at the end of the 8-week Treatment Period (Day 57), LDL-C will be measured for all patients by PUC¹.
- 3.4.1 Primary Efficacy Endpoint

Primary Analysis

The primary efficacy analysis is to evaluate the percent change from Day 1 to Day 57 in LDL-C (as determined by the Friedewald formula) for the combination therapy group compared to the placebo group. The percent change is calculated from Baseline to each measurement taken at Day 29, Day 57, and Day 85.

The percent change in LDL-C from Day 1 to Day 57 for each treatment is defined mathematically as μ_{jt} , where j stands for the jth treatment (*j*=0,1,2,3) and the subscript 0 refers to the placebo group; and *t* stands for time to visit at Day 29, Day 57, and Day 85 (*t*=1,2,3). The hypotheses testing to the percent change in LDL-C from Day 1 to Day 57 is then defined statistically as following:

 $H_0: \mu_{jt} - \mu_{0t} = 0, H_1: \mu_{jt} - \mu_{0t} \neq 0$, where *j*=1,2,3

NewAmsterdam Pharma BV	
Protocol TA-8995-303	

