The primary efficacy analysis of the percent change from Day 1 to Day 57 in LDL-C will be performed using a mixed model for repeated measures (MMRM) approach. The analysis will include fixed effects for treatment, visit, and treatment-by-visit interaction, along with a covariate of the Baseline value as a continuous covariate. It is to note that randomization was stratified by categories of LDL-C value (<3.5 mmol/L [<135 mg/dL] or \ge 3.5 mmol/L [\ge 135 mg/dL]) only to ensure similar distribution of LDL-C across all treatment groups; however, the MMRM model will include the original scale of the LDL-C value as a continuous covariate. The Restricted Maximum Likelihood estimation approach will be used with an unstructured covariance matrix. The least squares means, standard errors, and 2-sided 95% confidence intervals for each treatment group, for the pairwise comparisons of the combination therapy, obicetrapib monotherapy, and ezetimibe monotherapy to placebo, and for the pairwise comparisons of combination therapy and obicetrapib monotherapy versus ezetimibe monotherapy will be provided. The treatment comparison will be performed using a 2-sided test at the $\alpha = 0.05$ level of significance.

The MMRM approach will include all available assessments of percent change in LDL-C from Baseline to Day 29, Day 57, and Day 85. The model assumes the data are missing at random (MAR). If any data are missing, the model will use all information from the other time points to estimate the mean treatment difference at the given time point. No imputation of missing data will be performed for the primary efficacy endpoint analysis.

The analysis will be implemented using SAS[®] Proc Mixed. The sample SAS code can be found below:

Note: USUBJID = unique subject identifier TREATMENT = 0 (Placebo), 1 (Ezetimibe monotherapy), 2 (Obicetrapib monotherapy), 3 (Combination therapy) VISIT = visit BASE = Baseline value PCHG = Percent change from Baseline proc mixed; class USUBJID TREATMENT VISIT; model PCHG = TREATMENT VISIT; model PCHG = TREATMENT BASE VISIT TREATMENT*VISIT / solution cl; Repeated VISIT / TYPE=UN sub=USUBJID; Ismeans VISIT*TREATMENT / cl diffs; run;

Sensitivity Analysis

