Sensitivity analysis will be performed for the primary efficacy endpoint. In the first analysis, missing data will be imputed using a control-based pattern imputation model assuming the data are missing not at random (MNAR). The multiple imputation will be performed such that only observations from the placebo group are used to derive the imputation model for missing LDL-C values. Missing data at Day 29, 57, and 85 will be imputed using multiple imputation methodology in two steps. Initially, 25 data sets will be imputed for non-monotone missing values in the original dataset. In the second step the remaining monotone missing values will be imputed. Upon

completion of the trial, if the percentage of cases with incomplete data is larger than initially anticipated then the number of imputations will be increased for the final analysis.

The variables for the imputation model will consist of LDL-C values from Baseline and Days 29, 57, and 85. For each imputation dataset, the percent change from baseline to Day 57 will be analyzed using the MMRM model described above. The results from these 25 analyses will be combined to construct the treatment estimates using the parameter estimates and associated standard errors. Similarly, the difference of the adjusted treatment means (Combination therapy – Placebo) will be presented with the associated standard error and 95% confidence interval. Randomly chosen seed numbers will be selected for the analysis and will be retained.

In the second sensitivity analysis, the percent change from Day 1 to Day 57 in LDL-C, via the Friedewald formula, for the combination therapy group compared to the placebo group will be analyzed using an Analysis of Covariance (ANCOVA) model with fixed effects of treatment group and the Baseline LDL-C value as a continuous covariate. The least squares means, standard errors, and 2-sided 95% confidence intervals for each treatment group, for the pairwise comparisons of the combination therapy, obicetrapib monotherapy, and ezetimibe monotherapy to placebo will be provided. The treatment comparison will be performed using a 2-sided test at the $\alpha = 0.05$ level of significance. No imputation of missing data will be performed for this sensitivity analysis.

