3.4.3 Exploratory Efficacy Endpoints

Similar MMRM models will be used for the following analysis:

- Percent change from Day 1 to Day 57 in ApoB for the ezetimibe monotherapy group compared to the placebo group;
- Pairwise comparisons among the various treatment groups for the percent change from Day 1 to Day 57 in non-HDL-C, VLDL-C, HDL-C, TG, ApoE, and HDL-ApoE (with and without ApoC3);
- Pairwise comparisons among the various treatment groups for the change from Day 1 to Day 57, Day 1 to Week 12, and Day 1 to Week 16 in the mean trough plasma levels of obicetrapib; and
- Pairwise comparisons among the various treatment groups for the change from Day 1 to Day 57, Day 1 to Week 12, and Day 1 to Week 16 in CETP mass.

The proportion of subjects at Day 57 that achieve LDL-C <2.6 mmol/L (<100 mg/dL), LDL-C <1.8 mmol/L (<70 mg/dL), and LDL-C <1.3 mmol/L (<50 mg/dL) will be examined through Logistic Regression Models for binary variables with covariates of the treatment groups and the Baseline variable.

The Logistic Regression Model will be implemented using SAS[®] Proc LOGISTIC. The sample SAS code can be found below:

NewAmsterdam Pharma BV	CONFIDENTIAL	Statistical Analysis Plan		
Protocol TA-8995-303		Version V2.0, 24 June 2021		

Note: USUBJID = unique subject identifier TREATMENT = 0 (Placebo), 1 (Ezetimibe monotherapy), 2 (Obicetrapib monotherapy), 3 (Combination therapy) BASE = Baseline value LDLC100 = LDL_C value less than 100mg/dL at DAY57 (YES/NO) for example proc logistic data= LDL_C; Class TREATMENT(ref=0) / Param= Ref; Model LDLC100 = TREATMENT BASE / alpha=0.05 expb plcl plrl orpvalue lackfit; Ods output ParameterEstimates= Log_LDLC100_ParameterEstimates CLoddsPL= Log_ LDLC100_OddsRatios ; Run;

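### The contrast that shows what ezetimibe adds to obicetrapib (combination vs obicetrapib alone, percent change in LDL-C and ApoB) is promised in Protocol 1.4 but not pre-specified.

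*Protocol*

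**What the plan says.** The last paragraph of Protocol 1.4 gives the study's purpose: to find out whether ezetimibe further lowers LDL-C and ApoB beyond what a CETP inhibitor achieves. It then commits that "this study will test the effect of obicetrapib and ezetimibe combination therapy compared to obicetrapib monotherapy and ezetimibe monotherapy".

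The operative sections carry over only the ezetimibe half of that sentence:

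- **Endpoints and hierarchy** (Protocol 7; SAP 2.3.1, 2.3.2 and 3.4.2). The primary is combination versus placebo on LDL-C. Among the seven ordered secondaries, the combination meets an active arm twice, both times against ezetimibe. The last step is "Percent change from Day 1 to Day 57 in ApoB for the combination therapy group compared to the ezetimibe monotherapy group".
- **MMRM contrasts** (Protocol 9.2.1.1; SAP 3.4.1). These are the three active arms against placebo, and estimates "for the pairwise comparisons of combination therapy and obicetrapib monotherapy versus ezetimibe monotherapy will be provided".
- **Hypotheses** (SAP 3.4.1). Each arm is set against a reference, where "the subscript 0 refers to the placebo group". The ANCOVA sensitivity analysis likewise gives results "for the pairwise comparisons of the combination therapy, obicetrapib monotherapy, and ezetimibe monotherapy to placebo will be provided".
- **Exploratory endpoints** (Protocol 7; SAP 2.3.3). All-pairwise percent change covers non-HDL-C, VLDL-C, HDL-C, TG, ApoE and HDL-ApoE, but neither LDL-C nor ApoB. LDL-C enters only as target attainment: "Pairwise comparisons among the various treatment groups for the proportion of participants at Day 57 that achieve LDL-C <2.6 mmol/L" and two lower cut-offs. On these, Protocol 9.2.1.2 says "No adjustment will be made for multiplicity in testing the exploratory efficacy endpoints".

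The objectives (Protocol 2.1 to 2.3; SAP 2.1) name no combination-versus-obicetrapib comparison for LDL-C or ApoB. SAP 5 declares no departure from the protocol.

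**The concern.** Combination versus obicetrapib is the only pair that isolates ezetimibe's contribution on top of obicetrapib. Combination versus placebo gives the joint effect. Combination versus ezetimibe gives what obicetrapib adds. Both can be strongly positive when ezetimibe adds nothing.

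As the plan stands, the comparison that section 1.4 promises would surface for LDL-C and ApoB only as unlisted model output. Nothing says whether it is confirmatory, exploratory or incidental. SAP 4.2 says the end-of-treatment analysis will support regulatory interactions. A contrast whose status is settled after unblinding is open to the charge that it was chosen on the results.

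**Working it through.** **1. Which pairs are listed as percent-change endpoints** (Protocol 7; SAP 2.3)

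| Pair | LDL-C | ApoB |
|---|---|---|
| Combination vs placebo | primary | secondary 2 |
| Obicetrapib vs placebo | secondary 1 | secondary 3 |
| Ezetimibe vs placebo | secondary 6 | exploratory |
| Combination vs ezetimibe | secondary 4 | secondary 7 |
| Obicetrapib vs ezetimibe | secondary 5 | not listed |
| **Combination vs obicetrapib** | **not listed** | **not listed** |

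For LDL-C the five listed endpoint pairs are the same five that the MMRM contrast list names.

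**2. The plan's own power figure** (Protocol 9.2.5; SAP 2.2.4)

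Inputs: 25 per arm, difference 30 points, SD 15, two-sided 0.05.

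- SE of a difference = 15 × √(2/25) = 4.243 points.
- 30 / 4.243 = 7.07 standard errors, so power exceeds 99.99%.

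The stated power above 90% reproduces easily; about 6 per arm would suffice. It concerns combination versus placebo only.

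**3. Can the planned tests succeed if ezetimibe adds nothing?**

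Inputs: placebo 0; ezetimibe −18.58% (meta-analysis cited in Protocol 1.4); combination equal to obicetrapib; SD 15; 25 per arm; pooled t with 96 df; simulated trials.

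| Obicetrapib = combination | Combination vs placebo and vs ezetimibe both significant | All five LDL-C tests significant | Combination vs obicetrapib significant |
|---|---|---|---|
| −45.3% (earlier study, Protocol 1.3) | about 100% | 99% | 5% |
| −30% (the plan's combination-vs-placebo difference) | 76% | about 63% | 5% |

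The hierarchy places two ApoB steps before the last three LDL-C tests. The ApoB steps could not be simulated because no ApoB SD is given. The all-five figures are therefore upper bounds on passing every LDL-C test within the sequence.

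**4. Precision and power for the missing LDL-C contrast**

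95% CI half-width = t(0.975, 48) × 4.243 = 2.011 × 4.243 = 8.53 points.

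The documents give no expected difference for this pair, so the increments below are assumptions. They are the ezetimibe add-on to statin (15.1%) and ezetimibe monotherapy (18.58%), both from Protocol 1.4. Each is taken either as percentage points, or as a relative cut on the 100 − 45.3 = 54.7% of LDL-C that remains:

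- 0.547 × 15.1 = 8.26 points
- 0.547 × 18.58 = 10.16 points

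Power is from the noncentral t, two-sided 0.05:

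| True difference (points) | Two-arm t, SD 15, df 48 | Four-arm pooled, SD 15, df 95 | Residual SD 12.99, df 95 |
|---|---|---|---|
| 8.26 | 48% | 49% | 61%* |
| 10.16 | 65% | 66% | 78% |
| 15.1 | 94% | 94% | 98% |
| 18.58 | 99% | 99% | >99% |
| Difference with 80% power | 12.1 | 12.0 | 10.4 |
| CI half-width | 8.5 | 8.4 | 7.3 |

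*0.605 before rounding.

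The last column assumes that SD 15 is unadjusted and that baseline correlates 0.5 with the outcome: 15 × √(1 − 0.25) = 12.99.

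**5. ApoB.** No power can be given, because the documents state neither an ApoB SD nor an ezetimibe ApoB increment.

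**The case against.** The strongest reply is that one sentence of rationale is at odds with an otherwise consistent plan. Objectives, endpoints, hierarchy and contrasts agree with each other. Obicetrapib is the investigational product, and combination versus ezetimibe isolates its contribution. In Phase 2, which contrasts become confirmatory is largely the sponsor's choice. The pair is also partly covered already: it is an exploratory pairwise comparison for LDL-C targets and for percent change in non-HDL-C and other lipids. The `diffs` option in the SAP 3.4.1 sample MMRM code would print the LDL-C difference with its interval, and a similar model would do so for ApoB.

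Much of this is fair, and it limits the point to a gap between purpose and pre-specification. It does not remove the gap. The sentence in section 1.4 says what this study will test, and half of it did reach the hierarchy. Target attainment and non-HDL-C are not the measures named there. Printed output that no text lists has no status.

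Three supporting observations are weak evidence on their own:

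- The placebo-only hypotheses also omit the two ezetimibe comparisons that are in the hierarchy.
- Placebo-only ANCOVA contrasts are natural in a sensitivity analysis of the primary endpoint.
- The sample logistic code ("Class TREATMENT(ref=0) / Param= Ref") leaves every non-placebo pair needing an extra contrast, not only this one.

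The conclusion rests on the endpoint, hierarchy and MMRM lists.

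It is also fair that an added confirmatory step may be underpowered. That calls for a candid power statement and the last place in the sequence.

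**Conclusion.** The concern holds and should be fixed before unblinding. For percent change in LDL-C and ApoB, the comparison that section 1.4 says will be tested is not pre-specified anywhere, and no set of planned LDL-C tests answers it. With no added effect of ezetimibe, all five would still be significant in up to 99% of trials (45.3% scenario) or about 63% (30% scenario).

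The existing claim of power above 80% for the secondaries cannot be extended to this contrast. At 25 per arm and SD 15, 80% power needs a true difference of about 12 points, and power runs from 48% to 99% over assumed increments of 8.3 to 18.6 points. The textual finding depends on none of these assumptions. Existing tests remain valid and Type I error is unaffected.

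**What to change.** Before any unblinding:

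1. Add combination versus obicetrapib monotherapy to the MMRM contrast lists in Protocol 9.2.1.1, the synopsis and SAP 3.4.1.
2. Append two steps to the end of the fixed sequence: Day 57 percent change in LDL-C, then in ApoB, combination versus obicetrapib monotherapy. Make the change in Protocol 7, the synopsis, and SAP 2.3.2 and 3.4.2, with matching objectives in Protocol 2.2, the synopsis and SAP 2.1.2.
3. In Protocol 9.2.5, the synopsis and SAP 2.2.4, limit the statement of power above 80% to the existing secondaries. Say that the added LDL-C step has 80% power only for a true difference of about 12 points, and that the ApoB step has no power basis.
4. Add a combination-versus-obicetrapib contrast to the sample logistic code in SAP 3.4.3.

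The minimum alternative is to list both percent-change contrasts as pre-specified exploratory comparisons with nominal p-values and 95% CIs, and to reword section 1.4 to that status. This leaves the hierarchy and power statement untouched.

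The cost is wording, plus an entry in SAP 5 if only the SAP is amended. No data, visits or participants are added, and the sample MMRM code already computes the LDL-C estimate. Steps placed last take no alpha from the existing tests.

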#### 1.5 Risk/Benefit

Obicetrapib has undergone extensive nonclinical testing in the standard battery of tests according to International Council for Harmonisation (ICH) guidelines, including repeat-dose toxicity studies of up to 39 weeks duration. In addition, obicetrapib has been investigated in 8 completed clinical studies, of which 6 studies were in Phase 1 of clinical development and 2 studies were in Phase 2. A total of approximately 500 subjects have been exposed to obicetrapib in these studies. In Phase 1, a total of 159 subjects received single oral doses between 5 and 150 mg of obicetrapib, and 76 subjects received consecutive doses between 1 and 25 mg of obicetrapib for periods up to 28 days. In Phase 2, a total of 268 patients received 1 to 10 mg of obicetrapib for up to 12 weeks.

Obicetrapib has been shown to be a selective CETP inhibitor. In addition to shuttling cholesterol esters from LDL-C to HDL-C particles, obicetrapib has several additional compound-specific activities that are hypothesized to be beneficial in patients. A dose of 5 mg obicetrapib resulted in an LDL-C reduction of 45.3%, an ApoB reduction of 33.6%, an HDL-C increase of 157.1%, an

ApoA1 increase of 57.5%, and a significant increase in HDL-C efflux capacity.  This effect is considered important because it is expected to reduce established atheroma burden.

Single doses of obicetrapib up to 150 mg and multiple doses up to 25 mg administered over 28 days were generally well tolerated and safe in these studies. No clinically significant effects on vital sign measurements (systolic and diastolic blood pressure, heart rate, and body temperature), 12-lead electrocardiogram (ECG) findings, or results of safety laboratory tests or physical examinations were observed with obicetrapib treatment. In particular, no clinically significant changes in aldosterone, sodium, potassium, or bicarbonate concentrations were observed.

In addition, no dose-related effects have been observed on the type, frequency, or intensity of treatment-emergent AEs (TEAEs) in clinical studies of obicetrapib to date. In patient studies, most TEAEs were mild or moderate in severity. Of the patients with severe TEAEs, 2 were suspected to be related to both obicetrapib and statin treatment. The number of patients experiencing TEAEs and their severity were similar across all treatment groups. Incidence rates of drug-related TEAEs were also comparable for all treatment groups; the number of TEAEs in the obicetrapib treatment groups did not display a dose-dependent effect. There were 7 randomized patients with a treatment-emergent serious AE (SAE), none of which were suspected to be study drug related. One patient had treatment-emergent SAEs that resulted in study discontinuation. No deaths occurred during these studies.

